**Sponsor: University College London** 

### **Project summary:**

We will conduct a brief systematic review of sexual risk reduction behavioural interventions focussing on UK relevant evidence to identify a suite of effective behavioural interventions that can be combined to meet user's needs and are deliverable from SH clinic settings (Objective 1&2). We will review existing sexual risk assessment/triage tools using data reported to Public Health England (PHE) from SH clinics to develop/refine a tool that identifies individuals at increased behavioural risk (Objective 3). We will carry out a mixed methods study to describe sexual risk reduction practices in SH clinics in the UK and identify opportunities for intervention. This will include a survey of interventions offered in SH clinics, supplemented by key informant interviews among clinic staff (Objective 4). We will conduct interviews and discrete choice experiments among the potential target groups, to explore their experience and preferences for risk reduction interventions (Objective 5). Building on the results of the above work, we will propose individualised packages of behavioural interventions. The feasibility of delivery will be tested among clinic attendees and staff, while the user groups will provide feedback on the acceptability of the intervention overall and according to characteristics including age, gender, orientation, culture and ethnicity (Objective 6). A study will be undertaken to assess the acceptability and feasibility of implementation of this package of interventions and engagement with the elements of the interventions (Objective 7), and feasibility of conducting a RCT and collecting followup measures to assess the effectiveness of the intervention packages (Objective 8). The cost of the implementing the intervention will be estimated (Objective 9), and finally the triage tool and intervention manuals will be refined to ensure the fidelity of the interventions, and a trial design proposed for a full evaluation, if deemed feasible (Objective 10).

### Background

STIs continue to represent a major public health challenge in the UK. This is reflected in this commissioned call for the preliminary work required prior to the commissioning of a definitive study of the effectiveness of brief interventions to reduce sexual risk behaviour. Such interventions, while tested individually and in most cases showing a modest but consistent positive effect, have not been implemented systematically in a way that could have a population level impact in the UK. An additional challenge is that any implementation can only be sustainable if it can be delivered at minimal overall cost; this is not a time when substantial investment of additional resources across a large number of services is realistic. In this context, research is required now to identify brief, pragmatic, labour non-intensive interventions that can be tailored to the level of risk of the individual attending any of a range of different sexual health services. The characteristics of those in the higher risk groups will differ by clinic setting, gender, sexual orientation and other factors which will need to be incorporated into the intervention model. Finally, what is needed at this time is a test of the feasibility of conducting a definitive trial of effectiveness, incorporating an economic analysis.

#### Glossary

Throughout the protocol the term sexual health (SH) clinics is used to describe all types of clinical settings commissioned to provide sexual health services. This includes genitourinary medicine (GUM) clinics, sexual and reproductive health (family planning) clinics, and integrated contraception and sexual health services (CASH). Service users, or users, describe people who use SH clinics and health care providers (HCP) for the staff who provide the SH services.

### Aims and objectives

The project addresses the research question:

What is the feasibility of a randomised controlled trial of an individualised package of sexual risk reduction interventions offered at various points in the clinical care pathways within SH clinics (genitourinary medicine, contraception, and integrated sexual health clinics)?

The aims of the project are therefore:

1. To develop and pilot a package of evidence-based sexual risk reduction interventions for those at most risk, that can be implemented in SH services. The suite of interventions will be matched to service user's needs and developed alongside a triage method for identifying the appropriate target groups.

2. To assess the feasibility of testing the effectiveness of this individualised package of behavioural interventions in a randomised controlled trial (RCT) against usual care.

Specific objectives are as follows:

1. To review existing evidence relevant to the UK on the nature and efficacy of brief and self-delivered sexual risk reduction interventions.

2. To identify a suite of interventions of known effectiveness that can be delivered and combined to meet individual users needs.

3. To develop a sexual risk assessment/triage tool to identify service users' level of sexual risk and thus individualise packages of behavioural interventions to user's need.

4. To describe current practice in UK SH clinics with respect to delivery of sexual risk reduction interventions and identify best practice.

5. To explore opportunities and challenges to the delivery of candidate risk reduction interventions in SH clinics.

6. Using stakeholder input, to select, adapt and manualise an evidence-based suite of interventions that can be combined and delivered to meet individuals' needs.

7. To determine the acceptability, feasibility and deliverability of the individualised intervention packages in different SH clinical settings.

8. To assess the feasibility of testing the effectiveness of this individualised package of behavioural interventions in a randomised controlled trial (RCT) against usual care.

9. To estimate the cost and resource implications of implementing the individualised intervention packages in different SH settings.

10. To refine a manual of the intervention packages and to outline a feasible trial design (if feasibility is supported).

### Interventions to be assessed:

The selection of the suite of interventions will be informed by evidence on effectiveness, acceptability, feasibility and sustainability derived from a rapid literature review, building on existing reviews, and will use risk-reduction opportunities at several points in a clinical pathway.

Pending the results of the review in WP1, we anticipate that it will involve the following:

1. A triage step that stratifies individuals' sexual risk and thus allows an individualised package of interventions to be offered, tailored to the individual's needs according to a schema.

2. A package of intervention(s) that may comprise just one, or several components (or none in the case of those classified as at low risk).

3. Selection of a package of interventions with different modes of delivery, such as, but not limited to, group delivered (e.g. waiting room videos), self-delivered (e.g. interactive digital interventions), and clinician delivered (one-to-one motivational interviewing).

Interventions will be adapted from existing interventions as required, and selected for deliverability within existing resources and clinical pathways. The suite of interventions will be developed in conjunction with other initiatives to reduce STI incidence such as enhanced recall, designed to increase STI and HIV testing among those clinic attendees who have had an STI diagnosis or reported high risk sexual behaviours, and improved and facilitated partner notification, to reduce re-infection rates and detect undiagnosed infection in the community.

## **Research plan**

### Design and organisation of the project:

The project is a multi-stage mixed method study design that will incorporate a systematic review, secondary analysis of national surveillance data; interviews and surveys with clinic staff; semi-structured interviews, a discrete choice experiment and focus groups with clinic attendees; monitoring of intervention offering, uptake, and completion, and follow-up questionnaires; and capturing the clinical resources used. In order to achieve this, the study will be organised in 6 overlapping work packages.

The work packages (WP) are summarised as follows, with further details of each below:

WP1: A systematic review of sexual risk reduction behavioural interventions focussing on UK relevant evidence (Objective 1 & 2).

WP2: Develop a sexual risk assessment/triage tool to identify individuals at increased risk in sexual health settings (Objective 3).

WP3: A mixed methods study to describe sexual risk reduction practices and preferences in SH clinics in the UK and to identify opportunities for intervention (Objective 4 & 5).

WP4: To select and adapt a suite of evidence based interventions suitable for delivery in sexual health setting and acceptable to patients and staff (Objective 6).

WP5: To pilot the interventions, assess their acceptability, practicality, and cost of implementation; to assess the feasibility of a future randomised control trial (Objective 7-9).

WP6: To refine the triage tool, and manuals of the interventions to ensure that the triage tool can be incorporated into routine care (or derived from routinely collected data) and to ensure the fidelity of the interventions; to outline the trial design for a full evaluation (Objective 10).

The work packages and the corresponding objectives that they will address are detailed below:

## Work Package 1

**Objective 1:** To review existing evidence relevant to the UK on the nature and efficacy of brief and selfdelivered sexual risk reduction interventions

*Objective 2:* To identify a suite of interventions of known effectiveness that can be delivered and combined to meet individual users needs

Study design: A systematic review of the literature.

**Inclusion and exclusion criteria:** The inclusion and exclusion criteria will reflect the focus on intervention settings in the UK, or those with similar healthcare systems. It will include both interventions that can be delivered in sexual health clinics, (e.g. waiting room videos, brief one-to one behavioural interventions, such as motivational interviewing or cognitive behavioural interventions), and those that can be introduced in a clinic and then self-administered at home (e.g. interactive digital interventions).

**Search strategy:** The review by Scott-Sheldon included only RCTs carried out in the USA in STD clinics from 1989 to early 2009. The review will therefore need to have a broader scope, i.e. include non-US studies from high and middle income countries. The review will be restricted to RCTs. The review will start with a scoping review, after which the detailed review protocol will be finalised.

Peer-reviewed articles will be located using the following computerised databases: Cochrane Infectious Diseases Group trials register, Centre for Reviews and Dissemination (CRD), Database of Abstracts of Reviews of Effectiveness (DARE), MEDLINE, EMBASE, Web of Science, IBSS, LILACS, PsycINFO. Searches will cover the period 2000 to 2014. The database searches will be supplemented by scanning the reference lists of included papers.

We will use the latest standard criteria (CONSORT and STROBE) to assess quantitative study quality (Schulz et al 2010; von Elm et al 2008). All papers will be appraised independently by two reviewers. Where agreement is not obtained papers will be referred to a third reviewer.

**Data extraction:** A data extraction template will be developed focusing upon generic issues relating to design, definitions of standard care, barriers to uptake, characteristics of interventions (explicit/implicit operationalisation of theory) and populations, key aspects of process evaluation, and economic issues. We do not intend to search for full economic evaluations, but rather we will abstract relevant economic data from the identified studies, where reported. This will give us some indication of intervention costs. Analyses of intervention effectiveness will be recorded in accordance with the Preferred Reporting Items for Systematic reviews and Meta-Analyses (PRISMA) (Moher et al, 2009)).

**Outcomes:** The focus is on interventions that are designed to reduce sexual risk and so primary outcome measures will include reduction in a biological marker of sexual risk, for example incident HIV/STIs, or unwanted pregnancy, or a well validated behaviour measure (e.g. condom use, number of sexual partners). Length of follow-up and duration of effect will be recorded. Other outcomes of importance in informing the selection of front running interventions will be the resource implications, and acceptability to target groups.

**Outputs:** A suite of candidate interventions to be selected and adapted (in WP4) on the basis of outputs from WP3. These candidate interventions will be selected on the basis of effectiveness and deliverability within SH clinics and will be analysed in terms of their specified behaviour change objectives, underpinning mechanisms of change model, corresponding change techniques and implementation strategies in accordance with IM. The review will be registered on the PROSPERO database.

# Work Package 2:

*Objective 3:* To develop a sexual risk assessment/triage tool to identify service users' level of sexual risk and thus individualise packages of behavioural interventions to users' need.

**Study design:** Sexual risk assessment/triage tools will be developed to identify individuals at increased risk of STIs and HIV, through the analysis of routinely collected demographic, clinical and behavioural data that is entered into electronic patient records (EPR) as part of routine care in SH services and captured in the Genitourinary Medicine Clinic Activity Dataset (GUMCAD).

Statistical analysis of GUMCAD the latest version of which (GUMCADv3) will link individuals' sociodemographic, geographical, clinical and behavioural data with their incident or prevalent STIs (including HIV) will be undertaken to determine which factors best predict subsequent STI acquisition. GUMCAD is a pseudoanonymised patient-level electronic dataset which collects information on diagnosis made and other commissioned services provided by genitourinary medicine (GUM) clinics (level 3 services). The extension of GUMCAD to include information from other commissioned non-GUM sexual health services (level 2 services such as enhanced GPs, integrated contraception and sexual health services, young people's services e.g. Brook clinics, and other third sector or volunteer sectors services) is being rolled out (GUMCADv2). Collection and reporting of GUMCADv2 (n=570) from all level 2 and 3 services to PHE is mandatory; this therefore will be the **study population and setting** for this component of the analysis.

The **data collected** in GUMCADv2 includes basic demographic information (age, gender, self-defined ethnicity, country of birth, and sexual orientation) and residence (lower-level super output area of residence [LSOA] based on postcode), clinic information (which clinic and type of appointment), clinical information including all tests, vaccinations and diagnoses made for all patients seen. The STI diagnoses recorded include gonorrhoea or chlamydia including complicated and uncomplicated by site of infection), trichomonas, syphilis (including stage), genital herpes (primary or recurrent), genital warts (primary or recurrent), HIV and other blood borne viruses, and whether or not the patient was a contact of partner with an STI.

GUMCADv3 has been enhanced by the addition of key behavioural variables covering sexual risk and drug and alcohol use. These variables are based on those that the British Association for Sexual Health and HIV (BASHH) specialists recommend should be recorded as part of a routine sexual health consultation and those identified through on-going research on behavioural risk markers for subsequent HIV acquisition in MSM ([name] and [name]). The wording for these key behavioural questions has been informed by the National Survey of Sexual Attitudes and Lifestyles (Natsal). The behavioural data will be collected as part of the routine clinical history taken from the service user by the health care provider (HCP) and then reported back to PHE. This

provides the opportunity for developing STI risk algorithms using data on individual level self-reported (to HCP) sexual behaviour (including condom use), drug and alcohol use and previous STI diagnosis as well as socio-demographic and health service related data.

A sexual risk hierarchy will be defined using the data from GUMCADv3. Outcomes will be divided into low, medium and high risk based on the following assumptions; that infections characterised by a high proportion of symptomatic cases need higher risk sexual behaviour patterns for transmission to be maintained (Glaiser, 2006), and that in MSM the transmission of pharyngeal and urethral gonorrhoea and chlamydia can be sustained in the absence of unprotected anal intercourse.

- Low risk: no STI diagnosis
- Medium risk: chlamydia, trichomonas, or new episode of genital herpes, or new episode of genital warts only in heterosexual men and women. Pharyngeal or urethral chlamydia and gonorrhoea, or new episode of genital herpes or new episode of warts in MSM.
- High risk: more than one incident infection, gonorrhoea, syphilis and new HIV diagnoses in heterosexual men or women; rectal gonorrhoea, chlamydia, LGV, or syphilis, new hep C, or a new HIV diagnosis in MSM

**Data analysis:** Ordinal regression models to identify a parsimonious model of the key predictors of sexual risk according to the hierarchy above and thus the variables that an algorithm should take into account. These models will be informed by a social determinants framework (Monteiro et al 2005, Stenger et al 2013), which acknowledges the role of contextual factors, socio-demographic and geo-spatial (residence as well as clinic attended), in addition to self-reported sexual behaviour and drug and alcohol use to identify people at risk. The analysis (and thus the resulting models) will be disaggregated by gender, ethnicity and sexuality. The algorithm will be developed on a random sample of half the GUMCADv3 pilot dataset and then validated for performance on the remaining half.

**Sample size:** GUMCADv3 pilot data is being collected from 10 clinics, a mixture of types across England, from August 2013. The total number of patients seen annually in these clinics is approximately 140,000 with approximately 35,000 new STIs diagnosed. The large dataset will provide high power to detect associations and validate potential algorithms.

*Outputs:* the outputs of WP2 will include: A risk assessment tool which can be delivered via EPR. The acceptability and feasibility of the tool to identify individuals at three levels of risk in clinical settings will be piloted during WP5.

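### The triage tool's stated aim is to predict later STI acquisition, but its outcome is not required to come after the predictors, so the split-half validation cannot support that claim

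*Protocol*

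**What the plan says.** All of this is in the protocol, Work Package 2.

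- **Purpose (Study design).** The analysis of the surveillance dataset is intended "to determine which factors best predict subsequent STI acquisition".
- **Data linked (same sentence).** The newest version of the dataset connects each person's characteristics and behaviour with "their incident or prevalent STIs (including HIV". Behaviour is recorded by the provider while taking the routine history.
- **Outcome (risk hierarchy).** Levels are defined by diagnosis alone. The bottom level is "Low risk: no STI diagnosis". The middle level for heterosexual patients is "Medium risk: chlamydia, trichomonas, or new episode of genital herpes, or new episode of genital warts only in heterosexual men and women". The high level uses terms such as incident and new for some infections.
- **Model and validation (Data analysis).** Ordinal regression is used to find the "key predictors of sexual risk according to the hierarchy above". The algorithm is developed on a random half of the pilot dataset and validated on the other half.
- **Size (Sample size).** About 140,000 patients and about 35,000 new STIs a year, from 10 clinics.

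Neither here nor elsewhere does the protocol define an index attendance or a look-forward period, or require the diagnosis to come after the recorded behaviour.

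**The concern.** Predicting later acquisition requires an outcome dated after the predictors. A prevalent infection already exists when the history is taken, so it cannot be later than that history. If such infections enter the hierarchy, the model at least partly describes who is infected now. A person with high-risk behaviour and no infection on record sits in the bottom outcome level.

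The consequence reaches Work Package 5. A medium or high score makes a patient eligible for a risk-reduction package, and the piloted three-month follow-up asks about STIs diagnosed since the appointment. The tool is therefore used to direct prevention of future infection. If its validation is reported as evidence of predicting future infection, that claim goes beyond what was tested.

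**Working it through.** The protocol gives no power figure or effect size for this component, so there is no calculation to reproduce. The check sets the stated target against the outcome and the validation.

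1. **Target.** Acquisition after the time the predictors are observed.
2. **Outcome.** A level assigned from the diagnoses a patient has. Some categories carry the words new or incident. Chlamydia and trichomonas in the medium level, and gonorrhoea and syphilis in the high level, carry neither. Even a new diagnosis can be made at the visit where the history is taken, because new is not defined relative to that visit.
3. **Time order among inputs.** A previous STI diagnosis is listed among the algorithm's inputs, which implies some ordering. The text does not say what it is previous to.
4. **Validation.** Let Y0 be a diagnosis at the attendance where predictors are recorded and Y1 a diagnosis at a later one. As written, the hierarchy can contain both. A random split gives both halves the same mixture of Y0 and Y1, apart from chance. Performance in the second half therefore estimates how well the score tracks the mixture. Two scores with equal performance on the mixture can differ on Y1 alone, and the planned validation would not reveal it.

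**Counts in the document**

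- Diagnoses per patient per year: 35,000 / 140,000 = 0.25.
- Per half: 140,000 / 2 = 70,000 patients and 35,000 / 2 = 17,500 diagnoses.

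These are all diagnoses, not those made after a recorded baseline.

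**Feasibility of a strictly later outcome (assumed inputs)**

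The protocol gives neither the share of patients who re-attend (r) nor the share of re-attenders with a new STI (q). As assumptions only, take r from 10% to 30% and q from 5% to 25%. Later events = 140,000 × r × q.

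| r | q | Later events | Per half | As % of 35,000 |
|---|---|---|---|---|
| 0.10 | 0.05 | 700 | 350 | 2% |
| 0.20 | 0.10 | 2,800 | 1,400 | 8% |
| 0.30 | 0.25 | 10,500 | 5,250 | 30% |

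The range is wide and has no source in the protocol. It bears only on whether the fix is workable. At the low end, 350 events per half would be thin once split by outcome level and by gender, ethnicity and sexuality, as the Data analysis paragraph plans. At the high end they would be ample. The mismatch in steps 1 to 4 does not depend on these figures, and overall power is not the issue.

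**The case against.** The strongest reply is that the governing aim is Objective 3, which concerns a service user's level of sexual risk rather than a dated future event. The hierarchy is a deliberate proxy: Work Package 2 explains that infections are graded by the behaviour pattern needed to sustain their transmission. On that view the mismatch is with one clause. This stands in part. Diagnosis may serve Objective 3, and the hierarchy need not be abandoned. But the clause about later acquisition is in the protocol, and the planned validation cannot support it.

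A second reply is that index dates and time windows are usually left to an analysis plan. A plan could add them. The point here is not that a detail is missing. The protocol itself states an aim, an outcome and a validation that do not match.

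A reader might also infer three stronger things that the document does not support:

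- **That outcome and behaviour come from the same visit, so the tool is simply built for the wrong target.** The protocol never says so. The phrase about incident or prevalent infections describes what the dataset links, and several outcome categories refer to new or incident infection. Inclusion of current infections is the natural reading, given that no time rule is set, but it remains an inference.
- **That markers of current infection will crowd out behaviour.** The dataset does record "whether or not the patient was a contact of partner with an STI". That item appears in the list of recorded data and is not named as a candidate predictor, so its dominance cannot be asserted.
- **That a particular small share of the 35,000 diagnoses is relevant.** No such share can be obtained from the protocol.

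**Conclusion.** The point stands in a limited form. The stated aim is prediction of later infection, the outcome carries no time ordering, and validation on the same outcome cannot show that the tool meets that aim. It does not follow that the tool is useless or aimed at the wrong thing: as a classifier of current infection or risk level it may serve Objective 3 well.

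The size of the discrepancy cannot be estimated from the protocol. It depends on how many diagnoses in the pilot data follow a recorded attendance, and on whether the same variables predict current and later infection. The conclusion rests on the written definitions alone and would fall away if an index attendance and a look-forward rule were already fixed elsewhere. It should be settled before the tool is piloted in Work Package 5, because it determines what the validation can be said to show.

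**What to change.** 1. Define one index attendance per patient, take all predictors from it, and state a look-forward period. Calibration for later infection has no meaning without a time horizon.
2. Do all variable selection in the development half. Include there a check of the candidate variables against infections first diagnosed at a later attendance.
3. Leave the validation half untouched until the algorithm is fixed. Then report discrimination and calibration separately for diagnoses made at the index attendance and those made later. Feeding validation-half results back into variable selection would spoil the independent check.
4. If too few re-attendances can be linked, restate the aim as identifying current infection or level of risk, and remove the claim about later acquisition.

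**Cost.** Steps 1 to 3 are further analysis of the patient-level pilot data, provided attendances can be linked within a person over a useful period. The protocol gives no length of follow-up, so this needs confirming. Later infections are seen only in people who come back, so events will be fewer and the re-attending group is selected. That group should be described beside the results. Step 4 costs only a change of wording.

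### The triage model's outcome codes untested patients as low risk, which biases predictors linked to less testing towards looking protective

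*Protocol*

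**What the plan says.** All of this is in the protocol, mainly Work Package 2.

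- **Outcome.** The sexual risk hierarchy has three levels. Medium and high are lists of diagnoses. The lowest level reads, in full, "Low risk: no STI diagnosis". It carries no condition that a test was done.
- **Model.** The Data analysis paragraph uses this hierarchy as the dependent variable: "Ordinal regression models to identify a parsimonious model of the key predictors of sexual risk according to the hierarchy above".
- **Purpose.** The analysis is meant "to determine which factors best predict subsequent STI acquisition".
- **Records.** The dataset holds "clinical information including all tests, vaccinations and diagnoses made for all patients seen", so tests are recorded separately from diagnoses. Surveillance reporting is being extended to "level 2 services such as enhanced GPs, integrated contraception and sexual health services, young people's services e.g. Brook clinics", and the pilot data come from ten clinics of mixed type.
- **Predictors.** They include "contextual factors, socio-demographic and geo-spatial (residence as well as clinic attended", together with reported behaviour and drug and alcohol use. Models are run separately by gender, ethnicity and sexuality.
- **Validation.** "The algorithm will be developed on a random sample of half the GUMCADv3 pilot dataset and then validated for performance on the remaining half".

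Work Package 5 (Recruitment and sampling) makes only patients scored medium or high eligible to be offered the intervention.

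**The concern.** A patient can have no recorded diagnosis because tests were negative or because no test was done. The stated rule gives both the same code. What the model then predicts is infection multiplied by the chance of its being found, not infection alone.

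The named predictors include factors that plausibly track testing. A clinic whose attenders are tested less would look safer at equal true risk, and so would an area or an age group.

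Three features of the plan raise the stakes. Both halves of the data carry the same coding, so validation would reproduce the artefact and count it as good performance. The dataset is large, so a modest artefact would be statistically clear and likely to be retained. A low score also takes a patient out of the group that can be offered the intervention. If testing differs by clinic type, the Work Package 5 comparison of GUM with Brook clinics on the proportion scored medium or high would inherit the distortion.

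**Working it through.** The protocol states no figure for this point, so there is none to reproduce. It gives no testing rate and no prevalence in untested patients. What follows is an illustration under stated assumptions.

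**Figures in the protocol.** "The total number of patients seen annually in these clinics is approximately 140,000 with approximately 35,000 new STIs diagnosed". The ratio is 35,000 / 140,000 = 25 diagnoses per 100 patients. If each diagnosis were in a different patient, 140,000 − 35,000 = 105,000 would be coded low, tested or not.

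**Equal true risk.** Let two groups share true prevalence p, with tested fractions t1 and t2 and testing independent of infection within each group. The share coded above low is p × t. The apparent odds ratio, more-tested against less-tested, is [p·t1/(1 − p·t1)] / [p·t2/(1 − p·t2)]. The true value is 1.0.

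With p = 20% (assumed):

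| Tested | Share coded above low | Apparent OR |
|---|---|---|
| 90% vs 70% | 0.18 vs 0.14 | 0.2195 / 0.1628 = 1.35 |
| 80% vs 60% | 0.16 vs 0.12 | 0.1905 / 0.1364 = 1.40 |
| 90% vs 50% | 0.18 vs 0.10 | 0.2195 / 0.1111 = 1.98 |

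The choice of p matters little. At p = 25% the apparent odds ratio for the less-tested group is 0.73 for 90% vs 70% and 0.49 for 90% vs 50%. Inverted, these are 1.37 and 2.03. With 95% vs 90% tested it is only 0.93.

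**A real risk factor in a less-tested group.** Take prevalence 25% in a reference group tested at 90%, and a true odds ratio of 1.5 (prevalence 33.3%) in the other group. If that group is tested at 70%, the share above low is 0.233 against 0.225, and the apparent odds ratio is 1.05. At 50% tested it is 0.69.

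**Would the artefact be noticed as a signal?** One half of the data is 70,000 patients. For a predictor held by 10% of them (7,000 against 63,000), with p = 25% and 90% vs 80% tested, the comparison is 0.225 vs 0.200. Power at two-sided 5% exceeds 99%.

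**Untested patients at lower risk.** Keep 20% prevalence in tested patients and 90% vs 50% tested, and vary prevalence in the untested. True prevalence in a group is t × 0.20 + (1 − t) × untested prevalence.

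| Prevalence in untested | True prevalence | True OR | All-attendee coding | Tested only |
|---|---|---|---|---|
| 20% | 20% vs 20% | 1.00 | 1.98 | 1.00 |
| 10% | 19% vs 15% | 1.33 | 1.98 | 1.00 |
| 5% | 18.5% vs 12.5% | 1.59 | 1.98 | 1.00 |
| 0% | 18% vs 10% | 1.98 | 1.98 | 1.00 |

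The protocol's coding errs in one direction, by an amount that shrinks to zero as untested patients approach zero risk. Fitting to tested patients alone errs the other way in the same cases.

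**The case against.** The strongest reply is that the hierarchy gives short labels, not an analysis set. Tests and appointment type are recorded, so a restriction to tested patients could be laid down in an analysis plan that is not shown. That is possible. But the protocol does define the outcome, says which records exist and names the model. On that text an untested patient is coded low.

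The second reply is that untested patients may truly be at low risk, for example at contraception-only visits. This stands. In the last table, at 5% prevalence in the untested, the protocol's coding is 24% too high (1.98 against 1.59) and tested-only fitting is 37% too low (1.00 against 1.59). Neither coding can be assumed correct. The tool is also applied to all attendees, so training it on tested patients alone has its own selection problem.

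Three stronger readings are tempting, and the protocol does not support them:

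- A reader might infer that patients who never return are also coded low. The protocol links records to prevalent as well as incident infections and states no requirement for a later visit, so loss through non-return is conjecture.
- A reader might infer spurious odds ratios between genders, ethnic groups or orientations. The models are run separately by these factors, so such odds ratios are not estimated. What could shift is the baseline score within a less-tested stratum.
- A reader might want to require a chlamydia and gonorrhoea test of everyone. The hierarchy also contains warts, herpes and other infections, and warts or herpes may be diagnosed clinically. A blanket requirement could discard genuine medium-risk cases.

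**Conclusion.** The point holds as a bias of likely direction and unknown size. The stated outcome mixes infection with testing, and the planned validation cannot separate them. Predictors linked to less testing are pushed towards looking protective. It does not follow that they will look protective, because a strong true association can survive.

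The spurious odds ratios of 1.35 (90% vs 70% tested) and 1.98 (90% vs 50%) rest on assumed testing rates, an assumed 20% prevalence that is equal in tested and untested patients, and testing independent of infection within group. The bias is small if nearly everyone is tested, and it vanishes if untested patients carry no infection. The point deserves action because the data to examine it are already held and a low score removes eligibility for the offer.

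**What to change.** In the Work Package 2 hierarchy and Data analysis paragraph:

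1. Keep every patient with a recorded diagnosis, including one made clinically, in the medium or high category as now listed.
2. Code low risk only for patients with a relevant negative test and no new STI, and state by infection which tests count as relevant.
3. Treat patients with neither a test nor a diagnosis as outcome unknown: exclude them, or weight by the probability of being tested.
4. Fit and validate the model under both this coding and the all-attendee coding.
5. Report testing rates by clinic type and by predictor group.
6. Do not retain a predictor whose association appears only under the all-attendee coding without first checking whether it reflects testing.

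The cost is a revised definition, a second model fit and a table of testing rates, from fields that the protocol says are collected. The downside is fewer records and a model trained on a selected group while the tool scores all attendees. That is why both codings should be reported.
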